6.0 Consent process

6.1 Usability study

Consent will take place, after health workers have been recruited, in a private setting in the health facility. Members of the study team trained in the protection of human subjects will conduct the consent procedure. During the consent process, the study team will explain the purpose of the study and what involvement will entail. It will be emphasized that participation is voluntary and that their decision will not affect their employment in any way. The potential participant will have the opportunity to ask questions. Consent for

participation will be documented on a written informed consent form. The participant's understanding of the study and their potential involvement will be assessed with brief questions on the consent forms. One copy of the signed informed consent form will be provided to the participant and one copy will be kept for study records.

6.2 Diagnostic performance assessment

Consent will occur, after participant recruitment, in a private setting in the health facility or home. Members of the study team trained in the protection of human subjects will conduct the consent procedure. Study staff will review the study details with the volunteer. The potential participant will be given an opportunity to review the informed consent form and ask questions. Written consent or assent will be obtained from all participants. Parent permission will be obtained for all participants under the age of 18. Child assent will be obtained for all participants between the ages of 5 and 11 with one form (Appendix B4.1) and between the ages of 12 and 17 using another form (Appendix B4.2). Where appropriate, a conversational style oral presentation of consent information will be made in the local language to parents and children in order to account for any difficulties understanding written consent forms due to low literacy. Parents will confirm their permission for a child to participate in the study by signing or thumb printing on the consent forms. Children 5-17 will express their assent in writing in the presence of their parents as a witness, to ensure the assent process is without any coercion. The consent process will be conducted in Portuguese and consent forms were written in Portuguese and translated into English.

During the consent process, the study team will explain the purpose of the study and what involvement will entail. It will be emphasized that participation is voluntary and that their decision will not affect the care they receive in any way. The potential participant will have the opportunity ask questions. Consent for participation will be documented on a written informed consent form. The participant's understanding of the study and their potential involvement will be assessed with brief questions after the consent is reviewed. One copy of the signed informed consent form will be provided to the participant and one copy will be kept for study records.

If a potential participant is illiterate, an independent literate witness will be asked to join the consent process. This witness will be a health care worker or other family member uninvolved in the study. The study staff will read the consent form aloud to the potential participant and the witness will verify that the information read aloud matches the information written on the consent form. The witness will affirm that the study participant chose to be in the research study, that he or she was present the whole time the study was being explained, and that the participant had a chance to ask questions. The participant will get a copy of this form to keep. The witness will also sign the consent form.

7.0 Study products

7.1 SDB G6PD Analyzer

The STANDARD G6PD Analyzer is designed to measure the quantitative determination of total-hemoglobin concentration and G6PD enzymatic activity in fresh human whole blood specimen based on reflectometry assays. The test is intended to aid in the identification of people with G6PD deficiency. The test is currently registered in Brazil but not used by the public health system or considered part of routine use in malaria case management. PATH has conducted some initial laboratory evaluations which suggest that the test aligns to performance specifications outlined in the target product profile [19]. The test has CE mark and is registered for use in other malaria endemic countries.

Performance STANDARD G6PD test when stress tested under multiple temperature and humidity conditions. The STANDARD G6PD values were compared to the Pointe Scientific generated G6PD values for all 314 data points generated across the following ambient conditions: 22 °C, 32 °C 50% humidity, 37 °C 50% humidity, and 37 °C 75% humidity. ROC analysis was performed to generate the optimal thresholds for the STANDARD G6PD test. CI refers to the confidence interval, NA, not applicable.

Table 7. Performance of SD Biosensor STANDARD G6PD test

Threshold (Pointe Scientific value U/gHb)	Optimal STANDARD G6PD (U/gHb)	Sensitivity (95% CI)	Specificity (95% CI)
30% (2.8)	4.2	100 (95.1 – 100.0)	96 (93.0 – 98.3)
70% (6.5)	6.0	98 (92.4 – 99.7)	99 (96.8 – 99.9)
80% (7.4)	6.2	86 (80.7 – 93.9)	99 (95.9 – 99.7)
100% (9.3)	NA	NA	NA

Figure 4. SD Biosensor STANDARD G6PD Test

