3.2 Sample size

The sample size for this study is based on the expected prevalence of G6PD deficiency at the study site and by data requirements set by WHO PQ [15]. This requires obtaining samples from participants with a range of G6PD activity levels. The WHO PQ process defines these levels as such:

Table 2. G6PD activity thresholds

Females	
Deficient	G6PD activity < 30% of the adjusted male median
Intermediate	G6PD activity 30%-80% of the adjusted male median
Normal	G6PD activity > 80% of the adjusted male median
Males	

Deficient	G6PD activity < 30% of the adjusted male median
Normal	G6PD activity > 30% of the adjusted male median

According to the Target Product Profile (TPP), the novel POC G6PD will need to be at least 95% sensitive for detecting G6PD activity levels at 30% to 80% of normal enzyme activity. Assuming a sensitivity of 95%, with a confidence interval of 95%, and a 1% to 2% maximum marginal error, a minimum of 162 participants with deficient and intermediate G6PD activity will be needed. To account for any possible device/diagnostic failures or compromised blood samples due to insufficient blood, signs of blood degradation, or contamination, to the sample size will need to increase by 20%. In addition, to ensure there are sufficient deficient and intermediate participants in the case of a lower-than-expected enrollment rate of these two groups occurs, at least 200 participants of each group should be included in the study. This additional enriched sample will also serve to meet the requirements of the WHO PQ. Eligible adults and children aged 2 years old and above will be recruited for potential participation though diagnostic performance analysis will not be segmented based on age.

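### The 162 cases in section 3.2 give about ±3.4 points at 95% sensitivity, not the stated 1% to 2%, and Table 7 does not support 95% at the 80% threshold

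*Combined protocol and SAP*

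**What the plan says.** Section 3.2 gives the performance requirement: "the novel POC G6PD will need to be at least 95% sensitive for detecting G6PD activity levels at 30% to 80% of normal enzyme activity". It then sizes the case group: "Assuming a sensitivity of 95%, with a confidence interval of 95%, and a 1% to 2% maximum marginal error, a minimum of 162 participants" "participants with deficient and intermediate G6PD activity will be needed". An allowance for failed tests and compromised samples follows ("the sample size will need to increase by 20" per cent), and then a further enrichment target: "at least 200 participants of each group should be included in the study".

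Section 7.1 describes earlier laboratory work in hedged terms: "PATH has conducted some initial laboratory evaluations which suggest that the test aligns to performance specifications outlined in the target product profile". Table 7, in the same section, reports 314 data points from temperature and humidity stress testing, with cutoffs for the point-of-care test chosen by ROC analysis. Sensitivity is "100 (95.1 – 100.0") at the 30% threshold, 98% (92.4 to 99.7) at 70% and 86% (80.7 to 93.9) at 80%. The text does not comment on the 80% row.

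**The concern.** Two things in the sizing paragraph do not fit the rest of the protocol. The margin, the assumed sensitivity and the number of cases cannot all hold together. In addition, the assumed sensitivity equals the TPP requirement, while the only preliminary figure in the protocol at the 80% threshold is lower and has an upper limit below 95%.

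The 80% boundary is not peripheral. In Table 2 it separates intermediate from normal in females, and section 3.1.1 lists it among the analysis cutoffs. Someone relying on 3.2 would expect sensitivity for deficient plus intermediate participants to be known to within 1 or 2 points. With 162 analysable cases the interval would be roughly two to three times as wide as the looser of those figures. Someone relying on 7.1 would take the test to have met its specification at every threshold.

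**Working it through.** **Inputs.** From section 3.2: p = 0.95, a 95% interval (taken as two-sided, z = 1.96), margin d = 0.01 to 0.02, n = 162. From Table 7: the three sensitivity rows and their paired specificities, N = 314. From section 3.2 for expected yields: Brazil 100 deficient + 200 intermediate, Ethiopia 38 + 75, India 50 + 100.

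**1. The plan's own figure.** n = z²p(1−p)/d².
- d = 0.02: 3.8415 × 0.0475 / 0.0004 = 456.2, so 457.
- d = 0.01: 3.8415 × 0.0475 / 0.0001 = 1,824.7, so 1,825.

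The stated 162 is not reproduced. One-sided limits give 322 and 1,286. A finite-population correction returns 162 at ±2 points only for a population of about 250, which the protocol does not mention.

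**2. What 162 cases deliver.** Half-width = 1.96 √(p(1−p)/n).
- p = 0.95: 1.96 √(0.0475/162) = ±3.4 points.
- p = 0.885: 1.96 √(0.1018/162) = ±4.9 points.
- p = 0.86: 1.96 √(0.1204/162) = ±5.3 points.

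**3. Larger case counts.** The 20% allowance only protects the 162, so it does not change step 2. If more cases are analysed, the half-widths are:

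| Cases | p = 95% | p = 88.5% | p = 86% |
|---|---|---|---|
| 162 (stated minimum) | 3.4 | 4.9 | 5.3 |
| 300 (expected in Brazil) | 2.5 | 3.6 | 3.9 |
| 400 (200 of each group) | 2.1 | 3.1 | 3.4 |
| 563 (three countries: 300 + 113 + 150) | 1.8 | 2.6 | 2.9 |

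Only the three-country total, before any losses and with sensitivity at 95%, comes inside 2 points. None reaches 1.

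**4. Table 7 against the 95% figure.** At 30% and 70% the estimates (100% and 98%) exceed 95%. At 80% the estimate is 86% and the upper limit 93.9%, so the printed interval excludes 95%.

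**5. The 80% row against itself.** I searched all x/n with n from 20 to 314 for exact (Clopper-Pearson) limits that round to 80.7 and 93.9. The only match is 92/104 = 88.5% (80.71 to 93.89). The paired specificity interval (95.9 to 99.7) fits 207/210, and 104 + 210 = 314. Estimates near 86% at that size have other intervals: 89/104 = 85.6% gives 77.3 to 91.7, and 90/104 = 86.5% gives 78.4 to 92.4. The printed estimate and its interval therefore do not belong together under exact limits. Either way the printed upper limit stays below 95%.

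**6. Where the misses lie.** Under the same reconstruction the 80% row has 104 − 92 = 12 misses. The 70% row fits 91/93 at a cutoff of 6.0 (or 90/92). Any point below 6.0 is also below 6.2, so at least 91 of the 92 detected points lie below the 70% threshold. At most 1 of the 104 − 93 = 11 points between 70% and 80% was detected, and at least 10 of the 12 misses fall in that slice. With 73/73 detected below 30%, the 30% to 70% slice has at least (91 − 73)/(93 − 73) = 18/20 = 90%. With the alternative counts (74/74 and 90/92) it is 16/18 = 89%.

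**The case against.** The strongest defence is that 95% in section 3.2 is what the test must achieve, not what it is said to have achieved. Sizing at the required performance is a legitimate choice. Section 7.1 is hedged, and two of the three Table 7 rows are above 95%. This stands: the evidence shows that 95% is unsupported at one threshold, not that the plan is contradicted throughout. It does not rescue the margin, which fails at 95% itself.

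A second defence is that more than 162 cases will be recruited and data will be pooled across countries. That helps, as the table above shows, but section 3.2 ties the 1% to 2% margin to 162.

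Two stronger readings are tempting, and the documents do not support them.
- A reader might subtract the 30% row from the 80% row, get (92 − 73)/(104 − 73) = 19/31 = 61%, and conclude that the test misses intermediates generally. The 70% row shows otherwise: the misses cluster just under the 80% threshold, and detection between 30% and 70% is about 90%. The counts are also reconstructed, and the points span four ambient conditions, so they may not be independent.
- A reader might infer that the study is very unlikely to observe 95%, or that 86% or 88.5% should become the planning value. Table 7 rests on ROC-chosen cutoffs, stress conditions and a mostly deficient case mix (about 73 of 104). Section 3.1.1 sets cutoffs from an adjusted male median for each test, and the study expects 100 deficient to 200 intermediate. Sensitivity at a different cutoff and mix can move either way.

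**Conclusion.** The point holds for the stated precision and, more narrowly, for the planning value. With 162 cases the 95% half-width is ±3.4 points at the assumed sensitivity and about ±5 at the values Table 7 suggests, against a stated 1% to 2%. Two points would need 457 cases at 95%. At the 80% threshold the protocol's only preliminary evidence lies below 95%, so the assumption is unsupported there, and the alignment sentence in 7.1 is too broad for the table beneath it. The mismatch between the printed 86 and its interval is a background error and affects no endpoint or analysis rule.

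This rests on a two-sided interval, the normal-approximation half-width and independent cases. The 92/104 reconstruction also assumes exact limits and can be settled only from the source. The TPP is not among the documents, so its requirement is taken as section 3.2 states it.

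**What to change.** - **Section 3.2 (main change).** Replace the 1% to 2% margin with what 162 cases deliver, shown as a range: about ±3.4 points at 95%, ±4.9 at 88.5% and ±5.3 at 86%. Keep 95% as the TPP target to be tested, and do not substitute the Table 7 value for it. If a 2-point margin is meant to come from the pooled data, say so and give the pooled case count.
- **Section 7.1 (minor).** Limit the alignment sentence to the 30% and 70% thresholds and state that the preliminary estimate at 80% is below the target.
- **Table 7 (minor).** Check the 86 against its source and correct the estimate or the interval.

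The cost is wording and one recalculation. Recruitment and analysis do not change. The downside is a less favourable stated margin.

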7.2 Pointe Scientific

The Pointe Scientific will serve as the reference assay to assess G6PD activity. Its intended use is for the quantitative, kinetic determination of G6PD in blood at 340 nm. For in vitro diagnostic use only.

- A spectrophotometer capable of measuring at 340 nm with temperature controlled cuvette compartment is required to perform the assay
- To determine G6PD activity, which is reported in terms of grams of Hb or the number of RBCs, the Hb or RBC count must be determined separately from performing the G6PD assay. Calculations are then performed to obtain the G6PD activity. For purposes of this study, the G6PD activity from the Pointe Scientific kit will be calculated in terms of grams of Hb.
- US FDA cleared: k024006, Regulatory Class II, Product Code JBF.
- Approved as the predicate device for POC G6PD test evaluation by the US FDA.

7.3 Fluorescent Spot Test

The fluorescent spot test (FST) or TrinityBiotech G-6-PDH Screening test is widely used for in vitro diagnosis of G6PD deficiency using whole blood or dried blood spots. The G-6-PDH Screening test is a qualitative test performed by incubating a small amount of blood with glucose-6-phosphate and nicotinamide adenine dinucleotide phosphate (NADP). Drops of the mixture are removed at 5-minute intervals, spotted on filter paper and then viewed under long-wave ultraviolet light. Fluorescence is clearly evident in mixtures prepared from normal blood, whereas deficient samples yield little or no fluorescence. The test is affordable and produces qualitative, visual results in minutes. This test will represent a qualitative standard care test that is currently available and cleared by the FDA. The test will be performed according to PATH's guide to fluorescent spot testing for G6PD deficiency [20].

7.4 HemoCue

The HemoCue Hb 301 system is designed for quantitative POC whole blood Hb determination in primary care using a specially designed analyzer, the HemoCue Hb 301 Analyzer, and specially designed microcuvettes, the HemoCue Hb 301 Microcuvettes. The HemoCue Hb 301 System consists of a small and portable analyzer (photometer) and plastic microcuvettes. The microcuvette serves both as a pipette and as a measuring cuvette. A blood sample is drawn into the cavity by the capillary action. The filled microcuvette is inserted into the HemoCue Hb 301 Analyzer. The measurement takes place in the analyzer, which measures the absorbance of whole blood at a Hb/HbO₂ isobestic point. The system is factory calibrated and needs no further calibration.

7.5 Sysmex Hematology Analyzer

The Sysmex hematology automated analyzer is used to perform full blood counts and reticulocyte counts. This analyzer is registered and available for use in Brazil. It is used for research purposes routinely at the sites in Manaus and Porto Velho.

8.0 Benefit and risk considerations

8.1 Benefit to study participants

Participants in this study will have convenient access to a malaria test and a hemoglobin test. Malaria testing is available for free through the public health system. Hemoglobin testing and G6PD testing are not routinely offered as part of standard care. Participants who test positive for malaria or are found to be anemic will be counselled and referred to a local health worker or clinic for follow up and case management. Participants who have malaria will benefit from having their treatment informed by G6PD status, measured at the point of care, thus lowering the risk of severe hemolysis associated with standard vivax malaria treatment for G6PD deficient individuals, see Figure 3.

Participants in this study will have the opportunity to have their G6PD status tested by a reference assay. G6PD deficiency is a genetic condition that provides valuable clinical information for multiple clinical conditions beyond malaria treatment. If clinically relevant results are determined by the reference assay- that is G6PD activity is determined to be deficient or intermediate- participants will receive counselling regarding this information. G6PD testing will be offered to immediate family members of participants who are found to be G6PD deficient or intermediate free of cost.

The study team will test all family members with the FST, which will be more readily accessible both at the study sites and allow for faster results return. For females who test normal on the FST, the study team will follow-up with the gold standard test to determine if they are intermediate or normal, and provide appropriate counselling. This information may inform the care they receive for malaria in the future.

This research will also be advantageous for academic study and in the future for other people who will benefit from better G6PD tests and malaria treatment. Health workers will have the opportunity to receive training in the use of POC G6PD tests.

8.2 Risk and risk mitigation considerations

Study procedures do not represent significant risks to the participants beyond those that are associated with normal blood draw, such as pain, discomfort, feeling light-headed, fainting, and infection at the site of finger stick or venipuncture. The risks associated with blood draws will be mitigated through adherence to standard clinic procedures for infection control and through the use of research staff who have been trained in best practices for blood collection. The volume of blood drawn as part of the study procedures is within the safely limits recommended by the WHO and other organizations for both adults and children [21]. In the unlikely event of a research related injury, cost of treatment will be covered by the study. All decisions regarding clinical care or malaria case management will be made through referral to the local health care facilities.

There are no known reports of stigma associated with G6PD deficiency.

The study staff are at risk for exposure to blood-borne pathogens in the course of their work. All study team members will adhere to standard procedures for infection control. Study staff exposed to blood-borne pathogens during the course of their study roles will follow their institutional guidelines for post-exposure prophylaxis.

There is a minimal risk that health workers recruited for the usability study may feel compelled to participate in the study if their supervisor has recruited him or her. They may feel as though the usability study is intended to assess their performance rather than the usability of the test. We will mitigate these risks through the following measures:

- Study staff will ask supervisors to explain that participation in the study is voluntary and will not affect employment in any way.
- Consent procedures will be conducted in private to ensure confidentiality. During the consent procedure, participants will be informed that the aim of the study is to understand the user experience and the data will be used for purposes of product development only. The data will not be used to assess their competency or linked in any way to their job performance.

9.0 Study and safety monitoring

We anticipate that this evaluation poses minimal risk to participants, as it does not involve any medical intervention and blood draw volumes are within acceptable ranges. No data safety monitoring board will be used. PATH and the FMT/HVD and Fiocruz will conduct necessary staff training on study procedures prior to initiating the evaluation. Only trained users who have been certified as proficient in the use of the test will be involved in blood collection. The information participants will provide in the context of this evaluation is not considered sensitive and will not pose any significant risk to them personally or professionally.

The study team will be supervised by the local study lead. Study data will be aggregated into a database and a monitoring report will be generated every week, summarizing key indicators for study compliance. PATH and FMT/HVD and Fiocruz will hold weekly or

bi-weekly study review calls to discuss data collection and data quality to date. These indicators include but are not limited to the number of participants consented, the number of samples acquired, any deviations from study procedures, and corrective actions taken. This also includes any adverse effects related to blood sampling. Compliance indicators related to counselling and follow up discussed on this call will include:

- number of participants found to be G6PD deficient or intermediate by laboratory reference assay
- number of counselling cards delivered or picked up by participants found to be G6PD deficient or intermediate by laboratory reference assay
- proportion of participants found to be G6PD deficient or intermediate by laboratory reference assay that received appropriate counselling and counselling cards.

PATH will designate trained and qualified personnel to monitor the progress of this clinical study in accordance with Monitoring SOPs and the study-specific Monitoring Plan. Prior to study start, a study initiation visit will be conducted to provide training to site staff about the protocol, the completion of study documentation and data collection forms, the monitoring schedule, and all regulatory requirements. During the study, routine monitoring visits will be conducted to assure the site continues to adhere to the protocol, the investigator agreement, and regulations regarding conduct of clinical studies. Assessments will be made regarding the subjects' protection and safety, when relevant, as well as the quality, completeness, and integrity of the data.

